#### **6.2.4 Destruction of investigational product**

Local or institutional regulations may require immediate destruction of used investigational medicinal product for safety reasons. In these cases, it may be acceptable for investigational trial center staff to destroy dispensed investigational product before a monitoring inspection, provided that source document verification is performed on the remaining inventory and reconciled against the documentation of quantity shipped, dispensed, returned, and destroyed, and provided that adequate storage and integrity of drug has been confirmed. Written authorization must be obtained from the Sponsor or Sponsor designee after final accountability prior to destruction.

Unused trial medication from the site that has not been stored properly should not be destroyed until the monitor and/or Sponsor approve the destruction.

Written documentation of destruction must contain the following:

- Identity of investigational product(s) destroyed
- Quantity of investigational product(s) destroyed
- Date of destruction
- Method of destruction
- Name and signature of responsible person who destroyed the investigational products

Investigational sites that do not have a procedure for destruction and appropriate disposal of investigational product, or cannot dispose of investigational product locally may request assistance and documentation for return to the Sponsor, or assignment to a local qualified vendor for destruction and disposal.

### **6.3 MEASURES TO MINIMIZE BIAS: RANDOMIZATION AND BLINDING**

Allocation of patients to treatment groups will proceed through the use of an interactive web response system (IWRS) that is accessible 24 hours a day, 365 days a year.

The pharmacist or designee will be required to enter or select information that will include, but not be limited to: the user ID, and password, subject number, patient year of birth, as well as other information (as allowed locally). The pharmacist or designee will then be provided with a patient randomization number and treatment assignment. Once patient numbers and randomization numbers have been assigned, they cannot be reassigned. The randomization system will also send confirmation of the randomization, by email or fax, to the user. Specific instructions will be provided in the IWRS trial reference guide. Access to the randomization code will be limited; all Sponsor personnel (and representatives), and site personnel who are directly involved in the conduct of the trial will be blinded to randomization codes.

The treatment each patient receives will not be disclosed to the Investigator, trial center personnel, patients, or the Sponsor or representatives on the clinical study team. Further details for blinding and dispensing of blinded treatment are provided in the Pharmacy Manual.

If deemed by the Investigator to be medically necessary, the Investigator can unblind a patient via the IWRS.

## 6.4 STUDY INTERVENTION COMPLIANCE

Accountability and participant compliance will be assessed by maintaining adequate trial medication dispensing records and medication counts. The Investigator is responsible for ensuring that dosing is administered in compliance with the protocol. See [Section 6.2.3](#) for instructions on Drug Accountability procedures.

## 6.5 CONCOMITANT THERAPY

### 6.5.1 Prohibited medications

The following medications are prohibited for use during the trial:

- Concomitant use of any ***immunosuppressant medication***, other than CS and rituximab as described in this protocol. Patients who need other immunosuppressant therapy during the trial should be withdrawn. See [E 06, Section 5.2](#) for washout periods.
- Concomitant use of known ***strong to moderate inducers or inhibitors of cytochrome P450 (CYP) 3A*** (Appendix 7 [Section 12.7](#)) within 3 days or 5 half-lives (whichever is longer) of Day 1.
- Use of ***CYP3A-sensitive substrate drugs with a narrow therapeutic index*** (within 3 days or 5 half-lives (whichever is longer) of Day 1 including, but not limited to, alfentanil, astemizole, cisapride, cyclosporine, dihydroergotamine, ergotamine, fentanyl, pimozone, quinidine, sirolimus, tacrolimus (topical and oral), or terfenadine.
- ***Proton pump inhibitors*** are not permitted. Esomeprazole was shown to reduce the exposure of rilzabrutinib by approximately 50%, presumably due to the effects of a lack of an acidic environment on tablet dissolution. Subjects who are on proton pump inhibitors should be changed to histamine (H2) receptor blocking drugs if possible or not enroll in the trial. Details of H2 receptor blocker administration is provided in [Section 6.5.2](#).
- ***Intralesional steroids*** are not permitted within 3 months prior to Screening, during Screening and for the duration of the study.
- ***Warfarin*** use is not permitted within 1 week or 5 half-lives (whichever is longer) of Day 1 and for the duration of the study.
- ***Live vaccines***.

### 6.5.2 Particular permissible medications

The following medications are permitted for use during the trial:

- Local use of topical corticosteroids and oral corticosteroid rinses (mouth washes) are allowed.
- Use of short, defined courses of intravenous corticosteroids are allowed, if deemed clinically necessary and at doses consistent with the oral regimen, after consultation with Medical Monitor. Sites should make all attempts to use Sponsor-provided oral prednisolone during the Blinded Treatment Period.
- Bisphosphonate drugs for osteoporosis prophylaxis.
- Clinically relevant cytochrome P450 (CYP)3A substrate drugs that are not narrow therapeutic index (eg, “sensitive substrate” listed in Appendix 7 [Section 12.7](#)). These drugs should be managed by administering rilzabrutinib or placebo on a time schedule such that CYP3A substrate drugs can be given 2 hours or more after rilzabrutinib or placebo.
- Histamine 2 (H2) receptor blocking drugs (ranitidine or famotidine) and antacids are permitted provided they can be given 2 hours or more after administration of rilzabrutinib or placebo.

## **7 DISCONTINUATION OF STUDY INTERVENTION AND PARTICIPANT DISCONTINUATION/WITHDRAWAL**

### **7.1 DISCONTINUATION OF STUDY INTERVENTION**

#### **7.1.1 Permanent discontinuation**

The trial will be terminated if major safety concerns related to rilzabrutinib or placebo emerge. Trial safety stopping criteria are:

1. More than one rilzabrutinib-related death
2. Three or more life-threatening (Common Terminology Criteria for Adverse Events [CTCAE], Grade 4) rilzabrutinib-related TEAEs
3. Sponsor chooses to terminate the study (see [Section 7.1.2](#))
4. If the Data Safety Monitoring Board (DSMB) recommends trial termination due to safety reasons.

For participants in Germany, please see specific instructions in Appendix 10 [Section 12.10](#).

#### **7.1.2 Sponsor trial termination**

The Sponsor has the right to terminate this study at any time for any reason. Reasons for terminating the study may include but are not necessarily limited to the following:

- The incidence or severity of AEs indicates a potential health hazard to patients.
- Patient enrollment is unsatisfactory, and the Sponsor wishes to stop the study.
- New scientific knowledge or other conditions place study patients at undue risk by continuing in the study.
- If the DSMB recommends trial termination due to safety reasons.

After having informed the Investigators and the coordinators, the Sponsor may terminate the study before its scheduled term. The Institutional Review Board (IRB)/Independent Ethics Committee (IEC) and regulatory authorities will be informed according to local regulations.

### **7.2 PARTICIPANT DISCONTINUATION/WITHDRAWAL FROM THE STUDY**

#### **7.2.1 Patient Discontinuation and Stopping Rules**

The Investigator in conjunction with the Sponsor may also, at their discretion, discontinue the patient from participation in the study at any time if discontinuation would be in the patient's best interest. If a patient meets any of the criteria listed below, the patient should complete the assessments for the ET Visit (see [Table 2](#) and [Table 3](#)).

Reasons for discontinuing a patient may include, but are not necessarily limited to, the following:

- Severe and life-threatening pemphigus disease activity
- Grade 4 rilzabrutinib-related TEAE
- Serious allergic reaction to rilzabrutinib or placebo including anaphylactic reaction
- A patient in the Blinded Treatment Period requiring an additional “top up” dose of rituximab after their initial rituximab course of treatment or a patient in the Open-Label Extension Period or Long Term Extension Period requiring rituximab
- Human immunodeficiency virus (HIV)/acquired immune deficiency syndrome (AIDS), viral hepatitis (B and C) infection occurring during the study
- Pregnancy
- Any medical condition or personal circumstance that, in the opinion of the Investigator, exposes the patient to risk if the patient continues with rilzabrutinib or placebo or that prevents the patient’s adherence to the protocol
- If in the Investigator’s or the Sponsor’s judgment, discontinuation is in the patient’s best interest
- Violation of protocol inclusion or exclusion criteria, if, in the opinion of the Investigator and the Sponsor, the violation would significantly compromise data interpretation
- Discontinuation of the study by the Sponsor.

For participants in Germany, please see specific instructions in Appendix 10 [Section 12.10](#).

No follow-up or additional procedures will be performed on patients who discontinue before receiving rilzabrutinib or placebo. For patients who discontinue after receiving any amount of rilzabrutinib or placebo, the reason for a patient’s discontinuation from the study must be clearly documented in the patient’s medical records and on the appropriate page of the eCRF, and patients will be asked to complete the ET assessments (see [Table 2](#) and [Table 3](#)).

### **7.2.2 Patient withdrawal**

All patients have the right to withdraw consent and discontinue participation without prejudice at any time during the trial. Every effort should be made to comply with the protocol; however, patients will be withdrawn from the trial entirely with no further trial visits if any of the following situation arise:

- Withdrawal of patient’s consent or patient’s request to discontinue from the trial for any reason.
- The patient is unwilling or unable to comply with the protocol.

Patients who are withdrawn from the trial will not be replaced. The reason for the patient’s withdrawal from the trial should be recorded on the electronic case report form (eCRF).

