- e Hematology will include the following: hemoglobin, hematocrit, erythrocyte count (red blood cell [RBC] count), thrombocyte count (platelets), leukocyte count (white blood cell [WBC] count) with differential in absolute counts (including neutrophils, eosinophils, basophils, lymphocytes, and monocytes). Serum chemistry will include the following: aspartate aminotransferase (AST); alanine aminotransferase (ALT); total, direct, and indirect bilirubin levels; alkaline phosphatase (ALP); albumin; creatinine; urea; total protein; sodium; chloride; calcium; phosphate; potassium; and glucose (random). Creatine phosphokinase (CPK) is to be performed at Screening only. Coagulation will include: PT/INR, thrombin time, aPTT, and fibrinogen level and will be collected at Screening, Day 1 Week 1 Pre-dose, and Weeks 3, 5, 9, 13, 25, & 37. HbA1c and LDL level (fasting) will be collected every 3 months with GTI assessment.
- f Any woman of age  $\geq 55$  years with amenorrhea for  $> 1$  year, will be considered as having confirmed menopause and will not need FSH or pregnancy testing. Postmenopausal females  $< 55$  years of age (defined as amenorrhea  $> 1$  year) should have menopause confirmed by follicle-stimulating hormone (FSH) and serum pregnancy testing at screening. Surgically sterile females do not require any further confirmation of menopause and will not be considered to have reproductive potential.
- g Two hours post-dose ( $\pm 15$  minutes).
- h PK sample should be taken at random timepoints during the patient visits with as much variation in time since last dose as practicable. Time of draw will be captured as well as time of the last two rilzabrutinib or placebo doses, and time of the patient's last meal.
- i Pemphigus Clinical Response Definitions for CDA, CR, ECP, relapse/flare (refer to protocol [Section 3](#)).
- j For CS management, refer to [Appendix 1](#). At any point if CS needs to be adjusted between required visits, the patient may return for an unscheduled visit and additional CS may be dispensed via IWRS if required. CS doses taken will be recorded by the patient on a dosing diary. Patients should bring their diary and used and unused CS containers with them at every visit.
- k Rituximab may be administered intravenously during the Blinded Treatment Period, unless contraindicated, after a second "qualifying relapse/flare" occurs at or after Day 29 Visit. See [Appendix 1](#). Any rituximab dispensed will undergo drug accountability.

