#### 4.4 END OF STUDY DEFINITION

##### **End of Trial (Follow-up Period, 4 Weeks after last Trial Dose):**

End of Trial (EOT) for the overall clinical trial is defined as the point at which the last patient has completed the last visit of the study.

For patients eligible for the Long Term Extension, the EOT is defined as the point at which the patient has completed their Week 113 Visit (4 weeks after the patient's last dose of rilzabrutinib).

For patients that are not eligible for the Long Term Extension, the EOT is defined as the point at which the patient has completed their Week 65 Visit (4 weeks after the patient's last dose of rilzabrutinib).

Patients who are not able to complete the Blinded Treatment Period, Open-Label Extension Period or Long Term Extension Period as planned and discontinue the study early should be encouraged to come back for an Early Termination (ET) Visit as soon as possible. Patients that discontinue early will have the ET assessments completed as outlined in the Schedule of Assessments based upon from which phase treatment they are terminating, [Table 2](#) (Blinded Treatment Period), [Table 3](#) (Open-Label Extension Period), or [Table 4](#) (Long-Term Extension Period).

In addition to the ET Visit, patients should return for the EOT Visit 4 weeks following their last dose of rilzabrutinib/placebo or rilzabrutinib.

In the event the ET Visit occurs  $\geq 4$  weeks after their last dose of rilzabrutinib/placebo or rilzabrutinib, this will be recorded as the ET Visit and there is no need for the 4-week safety follow-up (EOT) visit.

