### **7.3 LOST TO FOLLOW-UP**

At the start of the study, the Investigator should try to obtain all relevant contact details for the patient to facilitate making contact with the patient, if necessary. In addition, each patient should be encouraged to attend all trial visits for which the patient is scheduled.

If a patient discontinues the study without notifying the Investigator, the Investigator must make every effort to contact the patient to identify the reason for the patient's discontinuation and to encourage the patient to complete the applicable ET visit assessments (see [Table 2](#) and [Table 3](#)). If documented attempts to contact the patient fail, and a reason for the patient's discontinuation is undiscoverable, the Investigator can declare the patient as "lost to follow-up" at the end of the study. The Investigator should document in the corresponding medical record all efforts to contact the patient.

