### **8.3.7 Early termination visit**

Please refer to [Table 2](#) (if terminating during double-blind treatment), [Table 3](#) (if terminating during Open-Label Extension), or [Table 4](#) (if terminating during Long Term Extension) for specific ET assessments. An attempt should be made to have the patient return for the ET Visit as soon as possible after the last dose of rilzabrutinib or placebo.

Patients in the OLE or LTE who are required to discontinue the study early per the rituximab receipt rules ([Section 6.2.1.3](#)) should have their ET Visit completed prior to rituximab infusion.

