### **8.6.3 Adverse Events**

#### **8.6.3.1 Adverse event collection period**

The AE Collection Period begins at the time of the first Screening/eligibility assessment and ends at the EOT for each patient.

During the COVID-19 pandemic, AEs will be collected during phone or video calls and recorded by electronic data capture (EDC) as described in [Appendix 9A](#) of the "Updated Guidelines to Sites for Delayed Patient Visits or Missed Visits Due to Travel Restrictions and Any Foreseeable Impacts of COVID-19" ([Appendix 9 Section 12.9](#)).

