#### **8.6.3.5 Treatment and follow-up of adverse events**

Adverse events (AEs), especially those for which the relationship to the rilzabrutinib or placebo is “related”, should be followed up until they have returned to baseline status or stabilized.

If after follow-up, return to baseline status or stabilization cannot be established an explanation should be recorded on the CRF.

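### Protocol 7.2.2 bars all further visits for some treated early leavers whom 7.2.1, 8.3.7 and 4.4 ask back for closing visits: a minor conflict affecting closing safety data, not the primary result

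*Protocol*

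**What the plan says.** Protocol 7.2.2 is categorical: "patients will be withdrawn from the trial entirely with no further trial visits if any of the following situation arise". Two bullets follow. The first joins withdrawal of consent with the patient's own request to stop, whatever the reason. The second is unwillingness or inability to follow the protocol.

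Other sections of the current protocol point the other way for early leavers:

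- **7.2.1.** Of those who discontinue after any amount of study drug, "patients will be asked to complete the ET assessments". No exception is made. The listed reasons include a medical condition or personal circumstance that keeps the patient from adhering.
- **8.3.7.** "An attempt should be made to have the patient return for the ET Visit as soon as possible after the last dose".
- **4.4, repeated in the synopsis.** Early leavers are encouraged to attend ET, and "In addition to the ET Visit, patients should return for the EOT Visit 4 weeks following their last dose". The EOT visit is waived if ET already falls 4 or more weeks after the last dose.
- **7.3.** For patients who leave without telling the site, the investigator is "to encourage the patient to complete the applicable ET visit assessments".

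On safety data, 8.6.3.1 says: "The AE Collection Period begins at the time of the first Screening/eligibility assessment and ends at the EOT for each patient". The SAP refers to ET in the timing of its analyses (4.3) and in the window for descriptive corticosteroid (CS) compliance (7.4).

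**The concern.** ET and EOT are both called visits in the protocol, so a ban on further trial visits covers them if read literally. A site can therefore find two incompatible instructions for the same treated patient, and nothing ranks them. With about 100 sites, practice may vary with the section a site consults.

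Ending all visits is right when a patient withdraws consent to follow-up. The difficulty is extending that rule to patients who have not done so. What is at stake is the closing safety assessment: scheduled labs, new non-serious adverse events between the last visit and EOT, and a final CS and lesion record.

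**Working it through.** The plan gives no figure on this point, so the check is mainly a comparison of texts.

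**1. Scope.** 7.2.1 rules out follow-up for patients who leave before any dose, so they raise no conflict. Only treated patients matter.

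**2. Instructions side by side.**

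| Situation of a treated patient | 7.2.2 | Other sections | Result |
|---|---|---|---|
| Withdraws consent to follow-up | No visits | 7.2.1 would still ask for ET | 7.2.2 is the proper rule |
| Asks to leave the trial | No visits | ET (7.2.1, 8.3.7); ET and EOT (4.4) | Conflict, unless the request is read as consent withdrawal |
| Unwilling or unable to comply | No visits | ET, with a near-identical reason listed in 7.2.1; ET and EOT (4.4) | Conflict; clearest for inability to comply |
| Leaves without notice | Not addressed | ET encouraged (7.3) | Different group, no direct conflict |

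The last row only shows the oddity: read literally, a patient who disappears is pursued for ET while one who asks to leave is not.

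**3. Source of each visit.** ET is in 7.2.1, 7.3, 8.3.7 and 4.4. The 4-week EOT visit for early leavers is only in 4.4 and the synopsis. Section 8.3.6 refers to Tables 3 and 4 for EOT content. Table 2, which governs the blinded period, has no EOT column.

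**4. Lost and kept under a literal reading.**

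- Lost: up to two visits per patient (one if ET would fall 4 or more weeks after the last dose). Adverse event collection formally runs to EOT, but no visit is left to carry it.
- Kept: serious event reporting (8.6.3.7.2), pregnancy reporting (8.6.4), repeat testing of unexplained clinically significant abnormal labs (8.6.3.6.1), and known adverse events, which "should be followed up until they have returned to baseline status or stabilized" (8.6.3.5).

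**5. SAP dependence.**

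- Primary endpoint: withdrawals are non-responders (Protocol 9.3.5, SAP 6.1.5.1). No ET data are needed.
- Time-to-event endpoints: censoring uses the last efficacy assessment on or before treatment discontinuation (SAP Tables 4 and 5).
- Cumulative CS: the time covariate runs to study discontinuation, first rituximab or the end of the blinded period, whichever is first (SAP 8.2).
- Treatment duration: the last visit date is used if the last dose date is missing (SAP 6.1.8, 7.4).
- CS compliance: the window for early leavers ends at ET (SAP 7.4). This is descriptive.
- Data cut: worded as Week 37 or ET (SAP 4.3).

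**6. Upper limit on time.** Let G be the longest scheduled gap in days, from the target days in SAP Tables 2 and 3, and add the 28 days from last dose to EOT. Blinded-period lab days come from Table 2 footnote e, where coagulation samples "will be collected at Screening, Day 1 Week 1 Pre-dose, and Weeks 3, 5, 9, 13, 25, & 37". Lab days for the two extensions come from the matching footnotes to Tables 3 and 4.

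| Period | Visit gap G | G + 28 | Lab gap G | G + 28 |
|---|---|---|---|---|
| Blinded | 225 − 197 = 28 | 56 | 169 − 85 = 84 | 112 |
| Open-label extension | 309 − 281 = 28 | 56 | 421 − 337 = 84 | 112 |
| Long-term extension | 589 − 505 = 84 | 112 | 589 − 421 = 168 | 196 |

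These are stacked worst cases: exit just before the next visit, last dose on the exit day, visit windows ignored, no unscheduled visit, and hematology and chemistry drawn on coagulation days because they share a table row. The G part is the ordinary schedule, which ET would have closed. Only the 28 days are post-dose observation that EOT would have covered.

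**The case against.** The best reply is that the sections can be reconciled. The ET and EOT wording is an invitation: patients are asked, encouraged, or should return. A sensible site could read 7.2.2 as ending the regular schedule while still offering an exit visit. The first bullet of 7.2.2 puts the request to leave beside consent withdrawal, and a request to leave the trial, rather than just the drug, can fairly be read as withdrawing consent. The 7.2.1 adherence reason is framed as the investigator's opinion. A patient who asks to leave is usually in contact with the site, which must record the reason, and during the pandemic adverse events may be collected by phone or video.

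Much of this stands. The request trigger is a conflict only on one of two fair readings, and literal loss of the visits is one reading of 7.2.2. Two things survive. The second bullet has no link to consent and overlaps 7.2.1 with the opposite instruction. And an invitation does not reconcile with a categorical ban: declining an offered visit is the patient's choice, while not being offered one is an effect of the protocol.

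A reader might also infer that all four of 7.2.1, 4.4, 7.3 and 8.3.7 require both visits. They do not: EOT for early leavers is in 4.4 and the synopsis alone, and 7.3 concerns other patients.

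**Conclusion.** There is a real contradiction in the current protocol text, of minor severity. It is firmest for treated patients who cannot comply, and conditional for those who ask to leave.

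Three stronger inferences are not supported:

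- **That the efficacy result is at risk.** The non-responder rule settles the primary endpoint without ET data, and the key secondary rules checked above have cut-offs that do not depend on ET. In the SAP, only descriptive CS compliance and the data-cut wording are shown to refer to it.
- **That safety follow-up ends.** Serious events, pregnancies, known events and significant abnormal labs are still followed.
- **That 56 to 196 days of safety data are lost.** Those are per-patient upper limits under stacked assumptions, mostly made up of the ordinary visit schedule outside the 56-day cases. They are neither event counts nor an estimate of bias.

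The documents give no exit rates by reason, so the number of affected patients cannot be stated. The conclusion assumes that at least some sites apply 7.2.2 as written.

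**What to change.** In 7.2.2, confine the rule of no further visits to patients who withdraw consent to follow-up. Direct every other treated patient who leaves early to the ET visit (7.2.1, 8.3.7) and to the EOT visit 4 weeks after the last dose (4.4, 8.3.6), keeping the existing waiver when ET already falls at or beyond 4 weeks. Add that patients leaving in the blinded period use the EOT assessments of Table 3, since Table 2 has no EOT column.

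No new visit or procedure is created, and the responder rule is unchanged. The cost is a short amendment needing IRB/IEC approval (10.2) across about 100 sites, so it is best bundled with the next planned amendment. The consent form changes only if it repeats 7.2.2. Some patients will still decline the visits.
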